2.3 Exploratory Objectives

- 1) To investigate and compare incidence of anemia and renal impairment among AF patients in relation to INR levels: under 2.0, 2.0-3.0, and over 3.0.
- 2) To investigate risk of stroke, systemic thromboembolic events, myocardial infarction, and bleeding events among AF patients in relation to discontinuation of warfarin treatment due to surgical operations and interventions.
- 3) To investigate how long it takes to achieve INR target in treatment initiators.
- 4) To investigate how well the INR target is maintained (TTR level).
- 5) To characterize the use of antiarrhythmic medication in AF patients at start of warfarin use and during warfarin use.
- 6) To characterize the use of medications with known interactions with warfarin in AF patients at start of warfarin use and during warfarin use.
- 7) To characterize comorbidity in AF patients using warfarin.

3 STUDY DESIGN

3.1 Overview of Study Design

The study with cohort design is conducted as a nationwide retrospective register-based linkage study using data obtained from the Finnish health care registers. The study population consists of all AF patients using warfarin with INR measurements in selected hospital district areas in Finland between 01-Jan-2007 and 3-Dec-2009.

Index date: Index date is defined as the date of first purchase of warfarin after 01-Jan-2007.

Follow-up period: Follow-up of the patients starts on the index date, and ends on 31-Dec-2011, at time of death or at time of emigration whichever occurs first.

History period: Treatment and comorbidity history is gathered from the period 01-Jan-2005 through 31-Dec-2006.

The key milestones of the study process are given below (Table 3.1-1). Note that the timelines are estimates only and are subject to change depending on the duration of the data permission processes and actual receipt of the data from the register holders.

Table 3.1-1: Study Timelines

Milestone	Anticipated date
Study protocol approved	4-Mar-2013
Registration in the ENCePP e-Register	30-Apr-2013
Ethics committee approval	30-Apr-2013
Data permit approvals	30-Jun-2013
Receipt of data from register holders	30-Sep-2013
Final study report	30-Dec-2013

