- Index date is defined as the date of first purchase of warfarin after 01-Jan-2007. Follow-up of the patients starts on the index date, and ends on 31-Dec-2011, at time of death or at time of emigration whichever occurs first. Treatment and comorbidity history is gathered from the period 01-Jan-2005 and 31-Dec-2006.

Data Analyses: Stratified incidence rates with 95% CIs will be estimated for each endpoint within the strata of the INR levels, time in therapeutic INR range (TTR) categories, and other covariates.

The crude and adjusted hazard ratio (HR) estimates with 95% CIs and P-values will be estimated within the INR levels and TTR categories using the conventional Cox's proportional hazards model adjusting for other covariates. For INR the category 2.0–3.0 will be used as the reference category. Similarly for TTR the category $\geq 60\%$ of time will be used as the reference category.

Sample Size/Power: According to the power calculations we are able to detect 10-20% differences in the main endpoints with sufficient power of approximately 80% or higher.

Limitations/Strengths:

- No exact prescribed dosages are available. Warfarin exposure is assumed based on the information of purchases and package sizes with defined daily doses (DDDs).
- Fully reliable information on eg, acetylsalicylic acid use is not available because the data of the prescription register exclude relatively inexpensive packages and over the counter medications which are not reimbursed.
- Medications used during hospitalizations are not available. However, based on the hospital care register the hospitalization periods can be taken into account to define gaps in the drug treatment periods.
- The laboratory data are collected from separate local central laboratories. Changes in places of domicile may affect the follow-up of the patients. On the other hand, previous published surveys on the subject have not included INR follow-up to this extent.

TABLE OF CONTENTS

TITLE PAGE	1
SYNOPSIS.....	3
TABLE OF CONTENTS.....	5
1 INTRODUCTION	7
1.1 Study Rationale.....	7
1.2 Research Question	7
2 OBJECTIVES.....	8
2.1 Primary Objectives.....	8
2.2 Secondary Objectives.....	8
2.3 Exploratory Objectives	8
3 STUDY DESIGN.....	8
3.1 Overview of Study Design.....	8
3.2 Study Population.....	9
3.2.1 Inclusion Criteria.....	9
3.2.2 Exclusion Criteria.....	9
3.3 Data Source/Data Collection Process	9
3.4 Definitions of Study Variables.....	11
3.4.1 Outcomes/Endpoint Variables	11

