3.2.1 Inclusion Criteria

Patients fulfilling the following criteria are included in the study:

- Patient has purchased warfarin (Anatomical Therapeutic Chemical classification (ATC) code B01AA03) between 01-Jan-2007 and 31-Dec-2009,
- Patient has at least one INR measurement available between 01-Jan-2007 and 31-Dec-2009, and
- Patient has a International Classification of Diseases (ICD-10 version 10) diagnosis code I48 for AF between 01-Jan-2005 and 31-Dec-2009.

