3.4 Definitions of Study Variables

3.4.1 Outcomes/Endpoint Variables

The studied primary outcomes/endpoint variables of interest are defined through ICD-10 diagnosis codes (hospitalizations and deaths) or ICD-O-3 codes (cancers). See [Appendix 1](#) and [2](#) for more detail.

The time to event for each primary outcome will be calculated as the time from the index date to the time of the diagnosis of the outcome when such an event occurs during the follow-up.

Index date is defined as the date of first purchase of warfarin after 01-Jan-2007. Follow-up of the patients starts on the index date, and ends on 31-Dec-2011, at time of death or at time of emigration whichever occurs first. Treatment and comorbidity history is gathered from the period 01-Jan-2005 to 31-Dec-2006.

Primary outcomes:

- Stroke
- Other systemic thromboembolic events excluding stroke
- Myocardial infarction
- Bleeding events
- Mortality all-cause
- Mortality (stroke)
- Mortality (myocardial infarction)
- Mortality (systemic thromboembolic events excluding stroke)
- Mortality (bleeding events)

The studied secondary outcomes/endpoint variables of interest are anemia and renal impairment.

Time to anemia is defined as the time from index date to time of first decrement of 20 g/L in haemoglobin or time when haemoglobin is under the reference value.

Time to renal impairment is defined as the time from index date to time when creatinine is under the reference value.

Secondary outcomes

- Anemia
- Renal impairment

In the statistical analysis follow-up for each time to event outcome continues until the time of the event, death, emigration or 31-Dec-2011 whichever comes first.

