4.1.1 Primary Objective

Objectives 1-3: Stratified incidence rates with 95% confidence intervals (CIs) will be estimated for each primary endpoint within the strata of the exposure variables (INR levels and TTR categories) and other covariates, including history of AF prior the index date.

The crude and adjusted hazard ratio (HR) estimates with 95% CIs and P-values will be estimated separately within the INR levels and TTR categories using the conventional Cox's proportional hazards model adjusting for other covariates. For INR the category 2.0–3.0 will be used as the reference category. Similarly for TTR the category $\geq 60\%$ of time will be used as the reference category.

The objectives will be evaluated separately for the prevalent warfarin user population and the new warfarin user population. The new warfarin user population consists of those patients who initiate warfarin treatment during the follow-up (01-Jan-2007 to 31-Dec-2009).

A further sensitivity analysis will be performed where the adjusted HRs are estimated stratifying by the history of AF prior to the index date.

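### Comorbidity history stops at 31-Dec-2006 for everyone, so conditions first recorded between then and a later index date are missing from the baseline covariates and risk scores of new users

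*Protocol*

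**What the plan says.** The history window is given three times with the same calendar limits:

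- Synopsis: "Treatment and comorbidity history is gathered from the period 01-Jan-2005 and 31-Dec-2006".
- Section 3.1: "Treatment and comorbidity history is gathered from the period 01-Jan-2005 through 31-Dec-2006".
- Section 3.4.1: "Treatment and comorbidity history is gathered from the period 01-Jan-2005 to 31-Dec-2006".

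The index date is patient-specific. Section 3.1 states: "Index date is defined as the date of first purchase of warfarin after 01-Jan-2007". Section 3.2.1 requires a purchase of warfarin (ATC "code B01AA03) between 01-Jan-2007 and 31-Dec-2009". Follow-up starts at the index date.

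Section 2.1 has the primary objectives evaluated separately in prevalent and new users. Section 4.1.1 describes the new users as "those patients who initiate warfarin treatment during the follow-up (01-Jan-2007 to 31-Dec-2009"). Hazard ratios for INR level and TTR category are estimated "using the conventional Cox's proportional hazards model adjusting for other covariates".

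Section 3.4.3 lists those covariates. They include CHADS2, CHA2DS2-VASc, prior stroke, transient ischaemic attack, heart failure, diabetes, hypertension, vascular disease and cancer. Neither that section nor Appendix 4 gives them a look-back of their own. Section 4.1 describes the population at baseline, which it equates with the start of follow-up.

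**The concern.** The window is tied to the calendar and the baseline is tied to the patient. The two meet only for someone who enters at the very start of 2007. For a later entrant, a diagnosis made after 31-Dec-2006 but before the first warfarin purchase is too late to be history and too early to be follow-up. A patient with a first recorded stroke or heart failure diagnosis in 2008 who starts warfarin in 2009 would be coded as free of that condition, with a CHADS2 score to match.

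New users are affected most, because they are by definition spread over 2007-2009. Prevalent users buy warfarin repeatedly and should mostly have their index purchase early in 2007. The protocol reports the primary objectives separately for these two populations, so the quality of the adjustment set would differ between the two sets of results. The 90-day analysis after initiation (section 4.1.2, objective 1) uses the same covariates in initiators and inherits the problem.

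**Working it through.** **Inputs.** History window 01-Jan-2005 to 31-Dec-2006 (synopsis, 3.1, 3.4.1), which is 730 days. Index date: first purchase after 01-Jan-2007 (3.1). Latest index date: 31-Dec-2009, since a qualifying purchase must fall in 2007-2009 (3.2.1).

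**Step 1: uncovered time before index.** Gap = days from 01-Jan-2007 to the day before index. Available look-back = days from 01-Jan-2005 to the day before index. Share uncovered = gap / available look-back.

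| Index date | Gap (days) | Available look-back (days) | Share uncovered |
|---|---|---|---|
| 02-Jan-2007 | 1 | 731 | 0.1% |
| 01-Apr-2007 | 90 | 820 | 11.0% |
| 01-Jan-2008 | 365 | 1,095 | 33.3% |
| 01-Jul-2008 | 547 | 1,277 | 42.8% |
| 01-Jul-2009 | 912 | 1,642 | 55.5% |
| 31-Dec-2009 | 1,095 | 1,825 | 60.0% |

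The uncovered part is always the most recent part. For the last entrant it is the 36 months immediately before treatment.

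**Step 2: average gap.** Assumption: new users enter uniformly over 2007-2009. The mean gap is then about 36 / 2 = 18 months (1.5 years).

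**Step 3: share misclassified.** The protocol gives no rate at which comorbidities are first recorded before warfarin starts, so a range is assumed. With constant yearly rate r and gap t in years, the share of patients with no record before 2007 who are wrongly coded as free of the condition at index is 1 − exp(−r × t).

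| Assumed rate r per year | t = 1.5 years | t = 3 years |
|---|---|---|
| 1% | 1.5% | 3.0% |
| 2% | 3.0% | 5.8% |
| 5% | 7.2% | 13.9% |
| 10% | 13.9% | 25.9% |

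For example, 1 − exp(−0.05 × 1.5) = 1 − exp(−0.075) = 7.2%.

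**Step 4: what is outside the problem.**

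- A condition recorded in 2005-2006 is captured whatever the index date.
- Age and sex do not depend on the window.
- AF history is defined relative to the index date (4.1.1), and I48 codes are taken to 31-Dec-2009 (3.2.1).
- No warfarin purchase can lie in the gap, because the index date is the first one after 01-Jan-2007.
- Antiarrhythmic and interacting drugs are tabulated at the start of and during follow-up (4.1.3, objectives 5 and 6), and interacting drugs are defined over the warfarin treatment period (3.4.3).

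What remains is comorbidity history and the two risk scores built on it.

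**The case against.** The strongest reply is that the sentence says where history is gathered, not that later records are thrown away. It could describe the pre-cohort extraction period, with register data from 2007 onward added to it. Other wording is anchored to the patient: baseline is the start of follow-up, and AF history is taken before the index date. The timeline figure in section 3.3 is not reproduced in the text available, and section 4.1 leaves analysis detail to a separate SAP. This shows that the authors may have intended the right thing. It does not change what is written: no section extends comorbidity history to the index date, and an SAP that follows the stated window inherits the gap.

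A reader might infer three stronger things that the documents do not support:

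- *That the key confounders of late entrants are missed outright.* Only conditions first recorded in the gap are missed, and for someone entering in the first months of 2007 the gap is short.
- *That drug history is equally out of date.* The protocol takes drug use at the start of follow-up or during treatment, so the treatment half of the sentence does little harm.
- *That the INR and TTR hazard ratios are demonstrably biased.* INR level is a daily, changing category, and one patient can contribute time to all three levels. A miscoded comorbidity distorts the hazard ratio only so far as it is related to INR level or TTR after adjustment for the other covariates. The documents allow neither a direction nor a size to be derived.

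**Conclusion.** The point holds for comorbidity history and the risk scores in new users. As written, the rule does not reach the protocol's own baseline for anyone entering after early 2007, and the shortfall rises to 36 months for the last entrants. That much is calendar arithmetic and needs no assumption. The 18-month mean rests on uniform entry. The misclassified share, about 1.5% to 14% per condition at 1.5 years and 3% to 26% at 3 years, rests on assumed recording rates of 1% to 10% per year. That prevalent users are little affected rests on their refilling early in 2007.

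The consequence is possible residual confounding in the adjusted hazard ratios of a separately reported primary population, and unequal covariate quality between the two populations. This goes beyond detail left to the SAP, because the protocol states the window explicitly and the stated window produces the misclassification.

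**What to change.** In the synopsis and sections 3.1 and 3.4.1, replace the fixed end date: comorbidity history, CHADS2 and CHA2DS2-VASc are to be derived from all register records from 01-Jan-2005 to the day before each patient's index date. This closes the gap for everyone and loses nothing now captured.

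Add a sensitivity analysis with a fixed look-back of 24 months before index. That length is available to every patient, since even an index date of 02-Jan-2007 has 731 days behind it. It should not be the main definition: for anyone indexed in 2009 it would drop all 2005-2006 records, and for an index date of 31-Dec-2009 it would discard 1,825 − 730 = 1,095 days of available history.

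The downside of the main definition is that look-back length varies from about 2 to 5 years with entry date, so later entrants have more opportunity to have a condition recorded. The sensitivity analysis addresses this.

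The cost is a change of definition in three places and one additional analysis. The care register already has to supply diagnoses through 2011 for the outcomes. Because section 3.3 bases the data requests on the protocol, the sponsor should confirm that they cover all Appendix 4 conditions, including the cancer data, up to each index date.

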3.4.3 Other Covariates/Control Variables

- Reimbursement code 207
 - Yes/no
- Information about hospitalizations and institutionalization (other than hospitalization)

- dates
- will be taken into account when defining the discontinuation of warfarin treatment
- Laboratory parameters for anemia characterizations
 - Blood picture
 - ◆ Haemoglobin
 - decrement of 20 g/L
 - being under the reference value
 - See [Appendix 2](#) for details.
- Concomitant use of class D interactive drugs according to SFINX (Swedish, Finnish, INteraction X-referencing, see [Appendix 3, Table 3](#) for complete ATC listing)
 - Concomitant use during the warfarin treatment period assumed by the purchases and exposure (see definition for exposure in Section 4.1).
- Age*
- Gender*
- Hospital district
 - Helsinki, Turku, Tampere, Kuopio, Oulu, Jyväskylä
 - other possible central hospitals
- CHADS₂^{11 12}
- CHA₂DS₂-VASc^{11,12}
- Comorbidities (more in detail in [Appendix 4](#))
 - Hypertension*
 - Thyrotoxicosis
 - Cardiomyopathy
 - Congestive heart failure*
 - Diabetes*
 - Stroke*
 - Transient ischemic attack*
 - Vascular disease**
 - Cancer
 - Venous thromboembolism
 - *included in CHADS₂ score and in CHA₂DS₂-VASc score
 - **included in CHA₂DS₂-VASc score.

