5 STUDY LIMITATIONS/STRENGTHS

Finland has a well-developed population register system with tens of years of longitudinal follow-up data. The persons are identified in the registers with a unique personal identification number enabling linkage between different registers. These data has not been collected for study purposes, which may affect the quality of the data. However, these registers have been considered reliable for scientific research purposes.

Only those citizens that have been living in Finland for 12 months prior to index date will be included in the study.

No exact prescribed dosing information is available. Dosing is assumed based on the information of purchases and package sizes with defined daily doses (DDDs).

Coverage of the Prescription Register containing reimbursement information of all permanent residents of Finland is about 97%. Missing data includes relatively inexpensive packages which are not reimbursed. Fully reliable information on eg, acetylsalicylic acid use is then not available.

Medications used during hospitalizations are not available. However, based on the hospital care register the hospitalization periods can be taken into account to define gaps in the drug treatment periods.

No nationwide database about laboratory measurements is available. The laboratory data is then collected from separate local central laboratories. All laboratory values for particular patients may then not be available. Also changes in places of domicile may affect the follow-up of the patients. On the other hand, previous published surveys on the subject have not included INR follow-up to this extend.

To avoid selection bias, the cohort time (years 2007 to 2009) was chosen to avoid complication of patients switching from warfarin to newer anticoagulant medications eg, dabigatran.

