APPENDIX 4 COMORBIDITIES

Variable	Definition (ICD-10)
Hypertension	I10-I15
Thyreotoxicosis	E05
Cardiomyopathy	I420-I422, I429
Congestive heart failure	I50
Diabetes	E10-E14
Stroke	I63, I64, I693-I698
Transient ischemic attack*	G45
Vascular disease	I20-I25, I65-I66, I672, I70
Cancer	C00-C97, D00-D09
Pulmonary embolism	I26
Other venous thromboembolism	I80-183

ICD=International Statistical Classification of Diseases and Related Health Problems.

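### Comorbidity history opens on 01-Jan-2005, so even the earliest entrants have only two years of look-back, and older stroke, vascular disease, venous thromboembolism or cancer not coded again is recorded as absent

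*Protocol*

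**What the plan says.** The Synopsis, section 3.1 and section 3.4.1 give the same history period. Section 3.1: "Treatment and comorbidity history is gathered from the period 01-Jan-2005 through 31-Dec-2006". Section 3.4.1: "Treatment and comorbidity history is gathered from the period 01-Jan-2005 to 31-Dec-2006". One window serves both drug treatment and diagnoses, and no section gives a longer look-back for any condition.

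On entry, section 3.1 says: "Index date is defined as the date of first purchase of warfarin after 01-Jan-2007". Under section 3.2.1 the qualifying purchase can fall as late as 31-Dec-2009.

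Section 3.4.3 lists the comorbidities among the control variables. Age, gender, hypertension, congestive heart failure, diabetes, stroke and TIA are marked as "included in CHADS₂ score and in CHA₂DS₂-VASc score". Vascular disease is marked as part of CHA₂DS₂-VASc only. Cancer and venous thromboembolism are marked as part of neither score. Appendix 4 defines prior stroke as "I63, I64, I693-I698" and vascular disease as "I20-I25, I65-I66, I672, I70".

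Section 4.1.1 uses the covariates twice, as strata for the incidence rates and as adjusters in the Cox models. Exploratory objective 7 tabulates comorbidity.

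Section 5 says: "Finland has a well-developed population register system with tens of years of longitudinal follow-up data". It adds that a unique personal identifier links the registers. It does not mention the two-year look-back as a limitation, and no section gives a reason for it.

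**The concern.** A past stroke or TIA, established vascular disease, an earlier venous thromboembolism and an earlier cancer do not cease to be part of a patient's history because they happened before 2005. Under the stated window, a patient with a stroke in 2003 and no stroke code in 2005-2006 enters as having no prior stroke.

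Three outputs are exposed:

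- **Comorbidity tables.** Prevalences are too low. This needs no assumption about INR groups.
- **Scores and score strata.** A history item can add to a score but never subtract from it, so missed history can only lower CHADS₂ (through stroke, TIA and the other starred conditions) and CHA₂DS₂-VASc (through vascular disease as well). Some high-risk patients are then counted in low-score strata.
- **Adjusted hazard ratios.** If unrecorded history is unevenly spread over INR levels, part of its effect stays in the INR comparison for stroke, thromboembolism, bleeding and mortality.

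This concerns where the window starts. Its closing date, fixed at 31-Dec-2006 while entry runs on to 2009, is a separate matter, and moving it would not cure this one.

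**Working it through.** **1. Look-back by entry date.** The window from 01-Jan-2005 to 31-Dec-2006 is 2.0 years long.

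| Index date | Window start to index | Window end to index |
|---|---|---|
| 01-Jan-2007 | 2.0 years | 0 |
| 01-Jul-2008 | 3.5 years | 1.5 years |
| 31-Dec-2009 | 5.0 years | 3.0 years |

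The earliest entrant has exactly two years of history with no gap before index. If only the closing date were moved to the index date, look-back would run from 2 to 5 years by entry date, and the January 2007 entrant would still have two.

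**2. Share of prior strokes captured.** The protocol gives no figure, so these are assumptions: prior strokes spread evenly over the last Y years, and a fraction r of the older ones coded again in 2005-2006. For a January 2007 entrant:

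capture = 2/Y + (1 − 2/Y) × r, with r from 0 to 0.4

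- Y = 5: 0.40 to 0.40 + 0.60 × 0.4 = 0.64
- Y = 10: 0.20 to 0.20 + 0.80 × 0.4 = 0.52
- Y = 15: 0.13 to 0.13 + 0.87 × 0.4 = 0.48

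**3. Confounding left among patients recorded as having no prior stroke.** Let p be the true prevalence of prior stroke, s the share captured and h the hazard ratio for prior stroke, with no false positives. The prevalence of unrecorded stroke in this stratum is q = p(1 − s)/(1 − ps). The spurious ratio of INR under 2.0 to INR 2.0-3.0 is

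(1 + q₁(h − 1)) / (1 + q₀(h − 1))

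All inputs are assumed; none is in the protocol.

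*Set A: h = 2.5, p₀ = 0.20*
- p₁ = 0.25, s = 0.4: q₁ = 0.15/0.90 = 0.167, q₀ = 0.12/0.92 = 0.130; ratio 1.250/1.196 = 1.045
- p₁ = 0.25, s = 0.6: ratio 1.176/1.136 = 1.035
- p₁ = 0.30, s = 0.4: q₁ = 0.18/0.88 = 0.205; ratio 1.307/1.196 = 1.093
- p₁ = 0.30, s = 0.6: ratio 1.220/1.136 = 1.073

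*Set B: h from 2 to 3, s from 0.5 to 0.9*
- p₁ = p₀ = 0.20: ratio 1.00 throughout
- p₁ = 0.22, p₀ = 0.18: 1.006 to 1.041
- p₁ = 0.25, p₀ = 0.18: 1.011 to 1.073

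With s = 1 the ratio is 1.00 in every case.

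The upper end depends on the inputs. Step 2 allows capture below 0.4. With nothing captured, the most unequal case in set A tends to (1 + 0.30 × 1.5)/(1 + 0.20 × 1.5) = 1.45/1.30 = 1.115, which is simply the unadjusted confounding.

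**4. From the stratum to the overall estimate.** Patients recorded as having had a stroke carry no such bias under these assumptions. A hazard ratio pooled over both groups is therefore biased by less than the ratios in step 3.

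**The case against.** The strongest reply is that a two-year look-back, stated the same way three times, is a design choice and not a contradiction, and that it matches the 2005 start of the AF diagnosis criterion. That is so. The point is that the choice measures confounders less well than the registers appear to allow, and that the protocol neither justifies nor acknowledges it.

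Second, earlier disease is not always lost. The stroke definition includes the sequelae codes I693-I698, and vascular disease takes in the whole of I20-I25, so older events coded again in 2005-2006 are recovered. This stands, and it confines the point to history that is not coded again.

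Third, the size is assumed. Section 4.1 defines INR as a daily level, so one patient contributes person-time to several categories, which may make the imbalance in a fixed history item smaller than the inputs above. Other adjusters may absorb part of it. This also stands.

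Fourth, the remark in section 5 about decades of data is general, and no start year is given for any register or for ICD-10 coding. A fixed minimum, such as ten years, therefore cannot be supported from the protocol; asking for all available data can.

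A reader might go further and infer the following, none of which the protocol supports:

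- *All adjustment is too weak.* Age, gender, hospital district and drug use during treatment do not depend on the 2005 start.
- *Missed myocardial infarction, cancer or venous thromboembolism lowers both scores.* Infarction is not a covariate of its own. It enters only through vascular disease, which is in CHA₂DS₂-VASc alone. The other two are in neither score and affect adjustment only.
- *Most of the cohort are prevalent users.* Sections 2.1 and 4.1.1 analyse prevalent and new users separately but give no split.

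**Conclusion.** The point holds in limited form. The stated window gives even the earliest entrants two years of diagnostic history. Stroke, TIA, vascular disease, venous thromboembolism or cancer coded only before 2005 is then recorded as absent. Comorbidity prevalence is understated, the two scores can err only downward on this account, and the history-based adjustment is incomplete.

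The size and direction of any confounding cannot be derived from the protocol. Under the assumptions shown, with at least 40% of prior strokes captured, it runs from none to about 7-9% among patients recorded as having no prior stroke, and is less in the overall adjusted hazard ratio. It is zero if prior stroke is equally common across INR levels. For scale, section 4.2 claims adequate power for differences of 10-20%. A bias of several percent would matter at the lower end of that range, but it would not by itself produce such a difference. This is worth correcting but does not invalidate the study.

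**What to change.** In the Synopsis, section 3.1 and section 3.4.1, state two histories in place of one:

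- Drug-purchase history stays as it is, from 01-Jan-2005.
- For the Appendix 4 comorbidities, CHADS₂ and CHA₂DS₂-VASc, use all available ICD-10-coded care-register data, and all available Cancer Registry data, before each patient's index date. Confirm the first usable year with the register holders and state it.

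Keep the present two-year window as a sensitivity analysis, so that the effect of the longer look-back is visible. List the look-back length in section 5.

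The cost is modest: a few sentences of text and a wider date range in requests to register holders already named in Table 3.3-1. The timeline in Table 3.1-1 places protocol approval (March 2013) before data permits (June 2013) and data receipt (September 2013). The downside is a larger extract and a look-back that varies with index date, by up to three years between January 2007 and December 2009 entrants.
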